8.3.1 Required Concomitant Medications

- Female subjects of child-bearing potential must agree to use dual methods of contraception for the duration of the study and for at least 30 days after the last dose of carfilzomib. Male subjects must agree to use a barrier method of contraception for the duration of the study if sexually active with a female of child-bearing potential. Male subjects must also refrain from donating sperm for at least 90 days after the last dose of carfilzomib.
- Subjects should receive antibiotic prophylaxis with ciprofloxacin or other fluoroquinolone (or trimethoprim/sulfamethoxazole if fluoroquinolones are contraindicated). In addition, subjects should receive acyclovir or similar (famciclovir, valacyclovir) anti-varicella (anti-herpes) agent prophylaxis.
- Subjects should receive adequate granulocyte colony stimulating factor support on Day 8 of treatment.
- All subjects must receive prophylaxis with hydration as typically used for R-ICE per institutional guidelines.
- Subjects may be pretreated for nausea and vomiting with appropriate anti-emetics.
- Patients may receive transfusion support as per institutional guidelines.

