Study Design	This is multi-center open-label, prospective Phase I/Ib clinical trial evaluating the safety, efficacy, and pharmacokinetics/pharmacodynamics of Carfilzomib + standard R-ICE combination therapy in adult patients with relapsed/refractory diffuse large B-cell lymphoma. The statistical design is based on a dose-finding algorithm to determine the maximal tolerated dose (MTD) of the study regimen and an assessment of the efficacy of the treatment for patients as compared to an external standard, i.e., R-ICE historical control. All enrolled patients will receive the study drug and initiation of the treatment should take place as soon as possible following study enrollment. A total of up to 30 evaluable patients will be enrolled in the Phase I/Ib component
Target Accrual and Study Duration	A maximum of 21 patients for Phase I and 9 patients for Phase Ib expansion cohort will be enrolled at Roswell Park. The number of subjects required is a function of a currently unknown dose-toxicity relationship. Accrual is expected to take up to 10 years.
Study Procedures	
Disease Evaluation: Prior to study, at time of restaging; between Cycle 2 Day 15 to Cycle 2 Day 28 following Cycle 3 but before ASCT and at the end of treatment evaluation, then every 4 months (± 2 weeks) for 1 year, then every 6 months (± 2 weeks) for 2 years, then once a year (± 2 weeks) for 2 years for a total of 5 years, then as clinically indicated. The follow up period will begin at the end of study evaluation visit for patients that became ineligible for transplant for any reason but did not meet criteria for disease progression. The follow up period for patients that go on to transplant will begin at the Day +100 bone marrow biopsy. Patients that progress at any time will be followed for survival status only on a yearly basis.
 
Adverse Events: From first dose of study drug until 30 days after receiving last dose of study drug.
 
Hematology and Chemistry: Prior to study, Day 1 of each cycle, and post treatment follow-up.
 
Performance Status: Prior to study, Day 1 of each cycle, and post treatment follow-up.
 
History and Physical Examination: Prior to study, Day 1 of each cycle, and post treatment follow-up.
 
Electrocardiogram: Prior to study

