2. RATIONALE

Current standard salvage chemotherapy regimens (e.g., R-ICE, R-DHAP, etc.) used prior to HDC-ASCR in patients with relapsed/refractory DLBCL yield suboptimal outcomes. The ORR and CR response rate following salvage therapy with R-ICE or RDHAP is 63% and 38%

respectively. Moreover, the 3-year progression-free survival of relapsed/refractory DLBCL patients initially treated with R-CHOP and then salvage R-ICE or R-DHAP and HDC-ASCT is only 30%. The incorporation of active novel agents into the management of relapsed/refractory DLBCL is needed in an attempt to improve clinical outcomes.

A group of Roswell Park investigators has demonstrated that the ubiquitin-proteasome system plays an important role in the development of rituximab-chemotherapy resistance in B-cell lymphoma. Moreover, targeting the proteasome system with pharmacological inhibitors has resulted in significant anti-tumor activity in relapsed/refractory DLBCL. While the combination of bortezomib and systemic chemotherapy is currently being studied in patients with relapsed/refractory DLBCL, bortezomib is limited by its toxicity profile. Carfilzomib is a more potent and better tolerated proteasome inhibitor when compared to bortezomib. The study is seeking to determine the maximum tolerable doses of carfilzomib when administered in combination with the R-ICE chemotherapy regimen in relapsed/refractory DLBCL patients who are ASCT-eligible.

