9 STUDY PROCEDURES

9.1 Subject Registration

All data management will be conducted at Roswell Park. Eligible patients will be entered on study centrally at the institute by the Study Coordinator. Following registration, patients should begin protocol treatment within 14 days or sooner if clinically necessary. Issues that would cause treatment delays should be discussed with the Principal Investigator at Roswell Park (or

designee). If a patient does not begin protocol therapy within 14 days following registration, the patient's registration on the study may be canceled. The Study Coordinator should be notified of cancellations as soon as possible.

Table 3. Study Calendar

Tests and Observations	Prior to Study ¹	Day 1 of Each Cycle ²	At Time of Restaging ³	Collect Stem Cell and ASCT Data (if applicable) ²⁰	Collect Post ASCT Day +100 Data ²⁰	Post Treatment Follow-Up ⁴
History and Physical Exam	X	X				X
Pulse, Blood Pressure	X	X				X
Height/Weight/Body Surface Area⁵	X	X				
Performance Status	X	X				X
Drug Toxicity Assessment		X				X ⁷
Laboratory Studies						
CBC, Differential, Platelets	X	X ⁸				X
Serum Creatinine, BUN	X	X ⁹				X
Creatinine Clearance (Appendix C)	X	X ⁹				
Serum Electrolytes	X	X ⁹				X
Ca⁺⁺, Potassium	X	X ⁹				X
ALT, AST, Alkaline Phosphatase, Bilirubin	X	X ⁹				X
Phosphorus	X	X ⁹				
LDH and Uric Acid	X	X ⁹				X
EKG	X					
MUGA or ECHO	X					
HBsAg, HBcAb¹⁰	X					
HBV DNA, Qualitative	X ¹⁰					
HCV Ab	X ¹¹					
HIV (If risk factors present)	X					
Beta-2-microglobuline (B2M)	X					
Albumin	X	X				X

Serum or Urine-βHCG (female patients)	X ¹²					
Staging						
Lumbar Puncture	X ⁷	X ¹³				X ¹³
CT Scan (Chest/Abdomen/Pelvis) and/or PET	X ⁶		X			X ²³
Bone Marrow Aspiration and Biopsy	X ²¹		X ¹⁴			X ¹⁴
Histologic Review	X ²²					X ¹⁵
Cytogenetics (e.g., Bcl-2 or c-MYC studies)	X					X ¹⁵
Sample Submission and Correlative Studies						
Lymph Node Biopsy		X ^{16,17}				
Immune Biomarker Samples		X ¹⁸				
Pharmacokinetic /Pharmacodynamic Samples²⁴			X ¹⁹			
Adverse Events	X	X	X			X ⁷

- 1 To be completed within 28 days prior to enrollment
- 2 Within 48 hours prior to Day 1 of each induction treatment cycle.

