- 3 Prior to study, at time of restaging; between Cycle 2 Day 15 to Cycle 2 Day 28 following Cycle 3 but before ASCT and at the end of treatment evaluation, then every 4 months (\pm 2 weeks) for 1 year, then every 6 months (\pm 2 weeks) for 2 years, then once a year (\pm 2 weeks) for 2 years for a total of 5 years, then as clinically indicated. The follow up period will begin at the end of study evaluation visit for patients that became ineligible for transplant for any reason but did not meet criteria for disease progression. The follow up period for patients that go on to transplant will begin at the Day +100 bone marrow biopsy.
- 4 At least every 4 months (\pm 1 week) for 1 year, then every 6 months (\pm 1 week) for 2 years, then once a year (\pm 2 weeks) for 2 years for a total of 5 years from study entry, then as clinically indicated. The follow up period will start at the Day 100 bone marrow biopsy in patients that received a transplant. Patients that progress will be followed for survival status only on a yearly basis.
- 5 If there is a greater than 10% difference in weight from baseline, then recalculate the BSA prior to each treatment; otherwise the actual dose given does not need to change.
- 6 CT Scan to be completed within 28 days prior to enrollment
- 7 When clinically appropriate.
- 8 CBC with differential and platelet counts will be monitored 3 times per week in between cycles of C-R-ICE until count recovery.
- 9 Days 1, 2, 8, and 9
- 10 All patients must be screened for hepatitis B infection (HBsAg/HBcAb) before starting treatment. Patients tested positive for HBV surface antigen are ineligible. Patients tested HBsAg negative/HBcAb positive should have qualitative HBV DNA PCR testing. If HBV DNA is positive the subject is excluded. If HBV DNA is negative, subject may be included but must undergo at least every 2 months HBV DNA PCR

testing from the start of treatment throughout the duration the treatment course. Monitoring during the on treatment periods is required at least every 2 months and during follow-up at a minimum of every 2 - 3 months up to 6 months after the last dose. Prophylactic antiviral may be initiated at the discretion of the investigator.

- 11 All patients must be screened for HCV infection before starting treatment. Patients who test positive for HCV antibody (Ab) evaluation of LFT's and clinical evaluation to rule out cirrhosis.
- 12 To be completed within 7 days prior to enrollment.

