10.2 Imaging, Laboratory and Pathological Studies

Imaging, laboratory and pathological studies will be conducted for staging and response evaluation at baseline, between Cycle 2 Day 15 and Cycle 2 Day 28, and at the end of study evaluation following Cycle 3. Response to treatment will be evaluated according to the International Working Group Response criteria as reported by the revised Cheson criteria (Section 10.3).

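### Section 8.3.1 ties male barrier contraception to an undefined study duration, not to the last dose; on the narrower reading it lapses about 43 to 78 days before the sperm-donation ban ends

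*Combined protocol and SAP*

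**What the plan says.** One bullet in Section 8.3.1 sets three reproductive rules.

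- Women use two methods of contraception "for the duration of the study and for at least 30 days after the last dose of carfilzomib".
- For men sexually active with a woman who could become pregnant: "Male subjects must agree to use a barrier method of contraception for the duration of the study". Nothing follows about the time after the last dose.
- On donation: "Male subjects must also refrain from donating sperm for at least 90 days after the last dose of carfilzomib".

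Section 5.1.5 and inclusion item 15 of the eligibility checklist require male contraception but give no method and no duration.

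The protocol does not define when the study ends for a patient. Section 8.4, headed as the duration of treatment, limits time on study to three cycles. Section 10.2 places the last response imaging "at the end of study evaluation following Cycle 3", and Section 8.5 calls for end-of-study evaluations when treatment stops. The Synopsis describes the imaging at that point differently: "following Cycle 3 but before ASCT and at the end of treatment evaluation". Footnote 3 of Table 3 starts follow-up at the end-of-study visit for patients who become ineligible for transplant without progressing. For the others, "The follow up period for patients that go on to transplant will begin at the Day +100 bone marrow biopsy". Footnote 4 runs follow-up to five years from study entry.

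**The concern.** The male barrier rule is the only one of the three that is not anchored to the last dose, so its end depends on a term the protocol leaves open. If the study ends around Cycle 3, a man can comply fully, stop barrier use within weeks of his last dose, and still be barred from donating sperm under the same bullet.

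What is at stake is the protection of partners. Section 5.1.5 shows that the protocol has partner pregnancy in mind, since it asks a woman to report a pregnancy that arises while she or her partner is taking part. The regimen also contains ifosfamide, an alkylating agent (Section 6.3), and carboplatin, a DNA cross-linker (Section 6.4). No endpoint, sample size or analysis is involved.

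**Working it through.** The plan gives no figure for this point, so there is none to reproduce. The check counts the days of the 90-day donation ban on which no barrier rule applies.

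**Inputs**

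- Donation ban: 90 days after the last carfilzomib dose (Section 8.3.1).
- Cycle length: 21 to 28 days (Section 7.4.2.3).
- Last carfilzomib day in a cycle: assumed to be Day 9 or Day 2, because the schema figure is not shown in the text available. Day 9 is inferred from Table 3 footnote 9 (chemistry on Days 1, 2, 8 and 9), read with Section 7.3, which requires chemistry before each carfilzomib dose. Day 2 is the earlier alternative.
- Evaluation after Cycle 3: 0 to 21 days after the cycle ends. The upper limit comes from Section 13.5.2, which counts responses up to three weeks after the third cycle.

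**Formula**

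Uncovered days = max(0, 90 − d), where d is the number of days from the last dose to the end of the barrier duty. If the study ends with Cycle 3 or at the evaluation, d = (cycle length − last dose day) + days to the evaluation.

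**Results if the study ends with Cycle 3 or at the evaluation**

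| Last dose | Cycle length | Ends with Cycle 3 | Ends 21 days later |
|---|---|---|---|
| Day 9 | 21 | d = 12, uncovered 78 | d = 33, uncovered 57 |
| Day 9 | 28 | d = 19, uncovered 71 | d = 40, uncovered 50 |
| Day 2 | 21 | d = 19, uncovered 71 | d = 40, uncovered 50 |
| Day 2 | 28 | d = 26, uncovered 64 | d = 47, uncovered 43 |

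The range is 43 to 78 days. Where the duty ends with Cycle 3, the male tail of 12 to 26 days is also shorter than the 30 days set for women.

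**A man who leaves the study t days after his last dose, if the study means his own participation**

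Uncovered days = 90 − t, which is 90 at t = 0 and 76 at t = 14. A woman in the same position keeps 30 − t days: 30 and 16.

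**Wider readings**

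- Transplanted, with the study running to the Day +100 visit: the column heading "Collect Post ASCT Day +100 Data" is taken to count from a transplant given after Cycle 3. Then d is at least 100 and max(0, 90 − 100) = 0.
- Follow-up counts as study and the man stays in it: 0.
- The study means the whole trial, and it runs at least 90 days beyond his last dose: 0.

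**The case against.** The strongest reply is that the gap exists only on one reading of the term. Footnote 4 counts five years from study entry, and footnote 10 sets hepatitis B monitoring during follow-up to six months after the last dose; both suggest that follow-up belongs to the study. Section 4.2 uses study duration in its title for the trial as a whole. Section 2 describes the intended population as "relapsed/refractory DLBCL patients who are ASCT-eligible", so transplant is the planned path, and a study period running to Day +100 leaves no gap. The entry criterion in Section 5.1.5 has no end date and need not be read as stopping with treatment. The consent form, which was not available, may state a period.

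All of this stands as a limit on the claim, but it does not settle the term. Sections 8.4, 8.5 and 10.2 and footnote 3 place the end of study at or soon after treatment and before follow-up. If five years of follow-up counted, the 30-day clause for women would add nothing for anyone who stayed in it. A period stated in the consent form would help patients but would not alter the protocol rule.

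A reader might infer that early withdrawal produces a gap on any reading. The documents do not support that. Section 8.5 lists voluntary withdrawal among the reasons for stopping treatment, and stopping treatment is not the same as leaving the study. On the trial-wide reading, withdrawal would not end the duty at all.

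**Conclusion.** The point holds as a wording gap whose size depends on the reading. If the study ends with Cycle 3 or at the evaluation after it, about 43 to 78 of the 90 donation-ban days have no male barrier requirement. This assumes last carfilzomib on Day 2 or Day 9 and an evaluation 0 to 21 days after the cycle. The gap reaches 90 days for a man who leaves at his last dose, if the study means his own participation. It is zero if follow-up, the Day +100 visit or the whole trial counts.

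Three stronger statements are tempting and should not be made. The first is that the rule provides no cover after the last dose; on the wider readings it does. The second is that the gap is at least 60 days, by treating the 30-day adverse-event window in the Synopsis as the end of the study; no section says so, and the evaluation timing allows 43. The third is that the donation ban marks a proven period of risk to partners; that is an inference which the protocol does not state.

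Severity is low. Only men with a partner who could become pregnant are affected. Section 4.1 takes the Phase Ib dose from the Phase I results, so Phase I appears complete and new wording would reach at most the 9 expansion patients of Section 4.2, men and women together. Those patients may come from network sites, each of which would have to interpret the term.

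**What to change.** Amend Section 8.3.1 so that men sexually active with a woman who could become pregnant use a barrier method during treatment and for at least 90 days after the last carfilzomib dose, or longer if the sponsor's safety function so decides in view of the other agents. Put the same wording in Section 5.1.5 and inclusion item 15 of the checklist.

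The 90 days match the donation period already in the bullet. The documents do not settle the right length, which is a clinical decision. If the sponsor had intended the duty to last through follow-up, a 90-day minimum would shorten it, so the safety function should confirm the figure.

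The cost is one sentence plus matching text in two places, and a short extra period of barrier use for the men concerned. No visits, procedures or patients are added.

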8.4 Duration of Treatment

Subjects may remain on study for a maximum of 3 cycles.

8.5 Treatment Discontinuation

Upon treatment discontinuation all end of study evaluations and tests will be conducted. All subjects who discontinue due to an AE must be followed until the event resolves or stabilizes. Appropriate medical care should be provided until signs and symptoms have abated, stabilized, or until abnormal laboratory findings have returned to acceptable or pre-study limits. The final status of the AE will be reported in the subject's medical records and the appropriate eCRF.

Reasons for treatment discontinuation should be classified as follows:

- Death
- Progressive disease
- Treatment-related toxicity
- Toxicity unrelated to treatment
- Investigator judgment
 - The Investigator may withdraw a subject if, in his/her judgment, it is in the subject's best interest to do so.
- Noncompliance
- Subject voluntary withdrawal
 - A subject may withdraw from the study at any time, for any reason. If a subject discontinues treatment, an attempt should be made to obtain information regarding the reason for withdrawal.
- Early withdrawal of subject(s)
- Sponsor decision.

Subjects who are unavailable for follow-up evaluations should be classified as lost to follow-up for 1 of the following reasons:

- Lost to follow-up: For a subject to be considered lost to follow-up, the investigator must make 2 attempts to re-establish contact with the subject. The attempts to re-establish subject contact must be documented (e.g., certified letter).
- Death: Date and cause of death will be recorded for those subjects who die within 30 days after last dose of study drug (telephone contact is acceptable).

9 STUDY PROCEDURES

9.1 Subject Registration

All data management will be conducted at Roswell Park. Eligible patients will be entered on study centrally at the institute by the Study Coordinator. Following registration, patients should begin protocol treatment within 14 days or sooner if clinically necessary. Issues that would cause treatment delays should be discussed with the Principal Investigator at Roswell Park (or

designee). If a patient does not begin protocol therapy within 14 days following registration, the patient's registration on the study may be canceled. The Study Coordinator should be notified of cancellations as soon as possible.

Table 3. Study Calendar

Tests and Observations	Prior to Study ¹	Day 1 of Each Cycle ²	At Time of Restaging ³	Collect Stem Cell and ASCT Data (if applicable) ²⁰	Collect Post ASCT Day +100 Data ²⁰	Post Treatment Follow-Up ⁴
History and Physical Exam	X	X				X
Pulse, Blood Pressure	X	X				X
Height/Weight/Body Surface Area⁵	X	X				
Performance Status	X	X				X
Drug Toxicity Assessment		X				X ⁷
Laboratory Studies						
CBC, Differential, Platelets	X	X ⁸				X
Serum Creatinine, BUN	X	X ⁹				X
Creatinine Clearance (Appendix C)	X	X ⁹				
Serum Electrolytes	X	X ⁹				X
Ca⁺⁺, Potassium	X	X ⁹				X
ALT, AST, Alkaline Phosphatase, Bilirubin	X	X ⁹				X
Phosphorus	X	X ⁹				
LDH and Uric Acid	X	X ⁹				X
EKG	X					
MUGA or ECHO	X					
HBsAg, HBcAb¹⁰	X					
HBV DNA, Qualitative	X ¹⁰					
HCV Ab	X ¹¹					
HIV (If risk factors present)	X					
Beta-2-microglobuline (B2M)	X					
Albumin	X	X				X

Serum or Urine-βHCG (female patients)	X ¹²					
Staging						
Lumbar Puncture	X ⁷	X ¹³				X ¹³
CT Scan (Chest/Abdomen/Pelvis) and/or PET	X ⁶		X			X ²³
Bone Marrow Aspiration and Biopsy	X ²¹		X ¹⁴			X ¹⁴
Histologic Review	X ²²					X ¹⁵
Cytogenetics (e.g., Bcl-2 or c-MYC studies)	X					X ¹⁵
Sample Submission and Correlative Studies						
Lymph Node Biopsy		X ^{16,17}				
Immune Biomarker Samples		X ¹⁸				
Pharmacokinetic /Pharmacodynamic Samples²⁴			X ¹⁹			
Adverse Events	X	X	X			X ⁷

- 1 To be completed within 28 days prior to enrollment
- 2 Within 48 hours prior to Day 1 of each induction treatment cycle.
- 3 Prior to study, at time of restaging; between Cycle 2 Day 15 to Cycle 2 Day 28 following Cycle 3 but before ASCT and at the end of treatment evaluation, then every 4 months (\pm 2 weeks) for 1 year, then every 6 months (\pm 2 weeks) for 2 years, then once a year (\pm 2 weeks) for 2 years for a total of 5 years, then as clinically indicated. The follow up period will begin at the end of study evaluation visit for patients that became ineligible for transplant for any reason but did not meet criteria for disease progression. The follow up period for patients that go on to transplant will begin at the Day +100 bone marrow biopsy.
- 4 At least every 4 months (\pm 1 week) for 1 year, then every 6 months (\pm 1 week) for 2 years, then once a year (\pm 2 weeks) for 2 years for a total of 5 years from study entry, then as clinically indicated. The follow up period will start at the Day 100 bone marrow biopsy in patients that received a transplant. Patients that progress will be followed for survival status only on a yearly basis.
- 5 If there is a greater than 10% difference in weight from baseline, then recalculate the BSA prior to each treatment; otherwise the actual dose given does not need to change.
- 6 CT Scan to be completed within 28 days prior to enrollment
- 7 When clinically appropriate.
- 8 CBC with differential and platelet counts will be monitored 3 times per week in between cycles of C-R-ICE until count recovery.
- 9 Days 1, 2, 8, and 9
- 10 All patients must be screened for hepatitis B infection (HBsAg/HBcAb) before starting treatment. Patients tested positive for HBV surface antigen are ineligible. Patients tested HBsAg negative/HBcAb positive should have qualitative HBV DNA PCR testing. If HBV DNA is positive the subject is excluded. If HBV DNA is negative, subject may be included but must undergo at least every 2 months HBV DNA PCR

testing from the start of treatment throughout the duration the treatment course. Monitoring during the on treatment periods is required at least every 2 months and during follow-up at a minimum of every 2 - 3 months up to 6 months after the last dose. Prophylactic antiviral may be initiated at the discretion of the investigator.

- 11 All patients must be screened for HCV infection before starting treatment. Patients who test positive for HCV antibody (Ab) evaluation of LFT's and clinical evaluation to rule out cirrhosis.
- 12 To be completed within 7 days prior to enrollment.
- 13 Repeat as medically indicated if positive at baseline.
- 14 Document absence of disease at least once in CR if previously involved.
- 15 At the time of relapsed/refractory disease diagnosis.
- 16 If the patient is undergoing a pre-treatment fresh biopsy - collect tissue with a goal of at least 0.5 g (in saline or media (RPMI 1640) provided to pathology by Roswell Park Department of Medicine Lymphoma/Myeloma Laboratory; fresh tissue will not be collected from Network Sites
- 17 Repeat diagnostic lymph node/tumor biopsy if initial biopsy was not diagnostic. Do not repeat due to less than 0.5g of tissue being collected.
- 18 Refer to Section 9.3. To be drawn the day of the tissue biopsy.
- 19 Refer to Section 9.4 PK [pharmacokinetics] and 14.2 PD pharmacodynamics)[proteasome inhibition]Cycle 1 only
- 20 As per BMT services
- 21 BM biopsy and aspiration to be completed within 28 days prior to enrollment
- 22 If biopsy is completed at an outside facility or Network Site, a tissue block or slides will be submitted to the Roswell Park Pathology Department for central pathology review. In addition immunohistochemistry (IHC) for CD20, Ki67, CD10, Bcl-2, Bcl-6, and MUM-1 staining will be performed. Cell of origin will be determined according to the Han's algorithm as previously described. Samples may only be shipped to Roswell Park Monday-Thursday.
- 23 For patients within the first 3 years of follow up, CT scans will be ordered every other visit. Patients on annual follow up will receive a CT scan at every study visit until the end of year 5, then CT scans will be ordered as clinically indicated
- 24 PK/PD samples will be collected in Phase 1 only

